#### **3.8.2.9 Change in cGVHD Severity as Based on the Clinician-reported Global cGVHD Activity Assessment**

The Clinician-reported global cGVHD Activity Assessment is a 0-10 point numeric rating scale with a score of 0 indicating “cGVHD symptoms not at all severe” and a score of 10 being “Most severe cGVHD symptoms possible”. The activities are assessed on Day 1 of each cycle from Cycle 1 Day 1 to EOT.

Change from baseline in cGVHD severity based on the Clinician-reported global cGVHD Activity Assessment will be summarized as a categorical endpoint at all scheduled assessment visits.

#### **3.8.2.10 Change in Symptom Activity Based on cGVHD Activity Assessment Patient Self Report**

The cGVHD Activity Assessment-Patient Self Report is in [Appendix C](#). Activities are assessed on Day 1 of each cycle from C1D1 to end of treatment (EOT). The symptom activity item is a 0-10-point numeric rating scale with a score of 0 indicating “cGVHD symptoms not at all severe” and a score of 10 being “most severe cGVHD symptoms possible”. The status reported by subjects are categorized as none, mild, moderate, and severe. The comparison of cGVHD symptoms to a month ago will also be reported by subjects, ranging from -3 (very much worse) to +3 (very much better).

Changes in cGVHD symptoms based on global cGVHD Activity Assessment by the Patient Self Report will be summarized as a continuous endpoint at all scheduled assessment visits. Both scores as well as the change-from-baseline values will be presented.

The summary of the change-from-baseline of Global Severity Rating on categorical status and the summary of comparison of cGVHD to a month ago will also be presented.

The number and percentage of subjects reporting none, mild, moderate, and severe cGVHD will be summarized by visit.

### 3.8.2.11 Lee Symptom Scale Score (LSS)

The Lee cGVHD Symptom Scale Score (LSS) is the exploratory endpoint in this study.

The LSS (see [Appendix D](#)) will be assessed on Day 1 of Cycles 2-5, then on Day 1 of every other cycle thereafter and EOT. The questionnaire consists of 30 items over 7 domains: skin, eyes and mouth, breathing, eating and digestion, muscles and joints, energy, and mental and emotional. Each question is scored 0, 1, 2, 3, or 4.

A domain score will be calculated for each domain by taking the mean of all items completed if more than 50% were answered and normalizing to a 0 to 100 scale. A summary score will be calculated as average of all non-missing domain scores if more than 50% of them are non-missing. A higher score indicates more bothersome symptoms. A 7-point difference on the summary score of cGVHD symptom scale has been found to be clinically meaningful ([Lee et al., 2002](#)).

$$Raw\ Score = \frac{I_1 + \dots + I_m}{m}, \quad Domain\ Score = (Raw\ Score / 4) * 100$$

$$Summary\ Score = \frac{Domain\ Score_1 + \dots + Domain\ Score_n}{n}$$

In the above formulae, ‘m’ is the number of items that have non-missing values in a domain, and ‘n’ is the number of domains have non-missing domain scores.

The analyses will include:

- Both score and change-from-baseline values (summary score and domain scores) will be summarized as continuous variables by visit
- Number and percentage of subjects with a  $\geq 7$ -point reduction (7-PtR) from baseline (C1D1)
- Number and percentage of subjects with a 7-PtR from baseline on 2 consecutive assessments
- Duration of a 7-PtR (DO7-PtR) (defined as time from documentation of the first  $\geq 7$ -point reduction to the first documentation of less than 7-point reduction). If there are multiple episodes, then DO7-PtR will be measured as the sum of DO7-PtR from all episodes.

These analyses will be performed on mITT, Responder, and Non-responder Populations.

Descriptive statistics of domain, overall scores, and their change from baseline will be provided by cohort and visit.

#### **3.8.2.12 Pulmonary Function Tests (PFT)**

Five test variables of PFTs, Forced Vital Capacity (FVC), Residual Volume (RV), Diffusing Capacity of Carbon Monoxide (DLco), FEV1, and Total Lung Capacity (TLC) are collected from the CRF. Change from baseline values of FVC, RV, DLco, FEV1, and TLC will be summarized at each scheduled time point.

#### **3.8.3 Exploratory Endpoint**

Not applicable.

#### **3.8.4 Subgroup Analyses**

Subgroup analyses for the endpoints of ORR and DOR will be conducted for the following subgroups:

- Number of prior line therapies (1 vs.  $\geq 2$ )
- Number of organs involved at baseline ( $< 4$  vs.  $\geq 4$ )
- Baseline severity (severe vs. not severe, baseline activity assessment used as surrogate)

- Take concomitant medication proton pump inhibitor (PPI) on C1D1 (Yes/No)
- Refractory to most recent line of therapy prior to enrollment (Yes / No)

### **3.9 Safety Analysis**

Safety assessments will include AEs, serious adverse events (SAEs), vital sign measurements, clinical laboratory evaluations (hematology and chemistry), and electrocardiograms (ECGs). Unscheduled visits for safety assessments will not be presented in summary tables but will be in listings. All safety analyses will be performed using the safety population.

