--	--

	
action taken and outcome.
 
Laboratory results will be classified using the CTCAE v4.03 and summarized by treatment group. Incidence of laboratory abnormalities will be summarized. The worst on-study grade after the first dose of study drug will be summarized. The incidence of \geq Grade 3 laboratory abnormalities under treatment and shifts in toxicity grading from baseline to highest grade post-baseline will be displayed.
 
Vital sign measurements and ECGs will be summarized by treatment group at each scheduled time point using descriptive statistics and included in data listings.

--	--

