17.5. Safety Data

The primary safety endpoint is the percent of subjects experiencing AEs in Cohort 1 (200 mg QD), Cohort 2, (200 mg BID), and Cohort 3 (400 mg QD).

Safety assessments include AEs, SAEs, PEs, vital sign measurements, clinical laboratory evaluations (including TSH measurements), ECGs, PFTs, and reasons for treatment discontinuation due to toxicity.

Treatment-emergent AEs will be evaluated using the CTCAE v4.03. The secondary safety outcome will be the number and percent of subjects experiencing AEs overall. The total sample size of 16 subjects per KD025 dose group will provide > 90% probability of one or more KD025 subjects experiencing an AE that has an underlying rate of $\geq 14\%$ and > 80% probability of one or more subjects in the study experiencing an AE that has an underlying rate of $\geq 10\%$.

Treatment-emergent AEs will be summarized by treatment group using Medical Dictionary for Regulatory Activities (MedDRA[®]) System Organ Class (SOC) and preferred term, classified from verbatim terms. MedDRA[®] Version 20.0 or higher will be used. The incidence and percentage of subjects with at least 1 occurrence of a preferred term will be included. The number of events per preferred term will also be summarized. Causality (relationship to study treatment) will be summarized separately.

All AEs, SAEs, treatment-related AEs, treatment-related SAEs, \geq Grade 3 AEs, treatment-related \geq Grade 3 AEs, and AEs leading to withdrawal, or treatment discontinuation will be summarized overall and by treatment group according to SOC and preferred terms. AEs will also be presented in listings. Duration of AEs will be determined and included in listings, along with action taken and outcome.

Laboratory results will be classified using the CTCAE v4.03 and summarized by treatment group. Incidence of laboratory abnormalities will be summarized. The worst on-study grade after

the first dose of study drug will be summarized. The incidence of \geq Grade 3 laboratory abnormalities under treatment and shifts in toxicity grading from baseline to highest grade post-baseline will be displayed.

Vital sign measurements will be summarized by treatment group at each scheduled time point using descriptive statistics.

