### **3.1.4 Baseline**

Baseline value is defined as the valid and last non-missing value obtained within 28 days prior to subject receiving the first study medication, unless otherwise stated under the related assessment section. Baseline can be the day before the first study medication or on the same day as the first study medication if a pre-dose assessment is available. Subjects without data on a parameter before the first study medication will have a missing baseline for this parameter.

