### **3.9.2 Clinical Laboratory Evaluation**

The summary statistics (including number, mean, standard deviation, median, minimum and maximum) of all laboratory variables and changes from baseline will be calculated for each visit or study assessment by treatment group. For parameters of white blood cell counts, neutrophils (absolute count), lymphocytes (absolute count), monocytes (absolute count), hemoglobin, platelets, ALP, ALT, aspartate aminotransaminase, gamma glutamyl transferase, total bilirubin, glomerular filtration rate, plots of mean/mean changes from baseline with the corresponding standard error will be displayed.

For shift tables, laboratory results will be classified using the CTCAE Version 5.0. All graded laboratory parameters will be summarized separately for hematology and biochemistry. Corresponding shift tables comparing baseline to the worst post-baseline grade within the treatment period will be provided.

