### **3.9.3 Vital Signs**

Descriptive statistics for vital signs (weight, temperature, blood pressure, pulse rate, and respiratory rate) values and the change from baseline will be presented for each scheduled assessment time point.

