**Table 6. Safety TLFs**

T/F/L	Title	Population
T	Overview of subjects for safety analysis by cohort	Safety
T	Treatment emergent adverse events regardless of the relationship of study drug by primary system organ class, preferred term, maximum grade	Safety
T	Treatment-emergent adverse events related to the study drug by primary system organ class, preferred term, maximum grade	Safety
T	Treatment emergent serious adverse events regardless of the relationship of study drug, by primary system organ class, preferred term, maximum grade	Safety
T	Treatment emergent serious adverse events related to the study drug, by primary system organ class, preferred term, maximum grade	Safety
T	Treatment emergent adverse events leading to treatment discontinuation, regardless of the relationship of study drug, by primary system organ class and preferred term	Safety
T	Serious adverse events leading to treatment discontinuation, regardless of the relationship of study drug, by primary system organ class and preferred term	Safety
T	Adverse events with grade $\geq 3$ , regardless of the relationship of study drug, by primary system organ class and preferred term	Safety
T	Treatment emergent adverse events leading to treatment discontinuation, regardless of the relationship of study drug, by preferred term	Safety
T	Serious adverse events leading to treatment discontinuation, regardless of the relationship of study drug, by preferred term	Safety
T	Adverse events with grade $\geq 3$ , regardless of the relationship of study drug, by preferred term	Safety
T	Adverse events with any grade, regardless of the relationship of study drug, by preferred term	Safety
L	Listings of deaths, other serious and significant AEs	Safety
T	Summary of the worst on-treatment grade for hematology by cohort	Safety
T	Summary of the worst on-treatment grade for biochemistry by cohort	Safety
T	Hematology shift table based on CTC grade by cohort	Safety
T	Biochemistry shift table based on CTC grade by cohort	Safety
T	Change from baseline of PFT by visit and cohort	Safety
T	Change from baseline of hematology by visit and cohort	Safety
T	Change from baseline of biochemistry by visit and cohort	Safety
T	Change from baseline of urinalysis by visit and cohort	Safety

T/F/L	Title	Population
F	Liver function test: Mean ALT over time by cohort	Safety
F	Liver function test: Mean change from baseline of ALT over time by cohort	Safety

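### SAP 3.9 keeps unscheduled visits out of safety summary tables with no exception, at odds with the planned worst-grade and shift laboratory tables; separately, the SAP grades under CTCAE v5.0 where the protocol uses v4.03

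*SAP*

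**What the plan says.** SAP 3.9 lists laboratory evaluations among the safety assessments and then states: "Unscheduled visits for safety assessments will not be presented in summary tables but will be in listings". No exception follows in 3.9.1 to 3.9.4 or in Table 6.

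SAP 3.9.2 says of laboratory grades: "Corresponding shift tables comparing baseline to the worst post-baseline grade within the treatment period will be provided". Table 6 lists "Summary of the worst on-treatment grade for biochemistry by cohort" and "Biochemistry shift table based on CTC grade by cohort", with the matching pair for hematology. By contrast, SAP 3.9.3 says that vital signs summaries "will be presented for each scheduled assessment time point", so the SAP does write the restriction out in at least one place.

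The Statistical Analysis part of the protocol synopsis says: "The worst on-study grade after the first dose of study drug will be summarized". Protocol 17.5 repeats this and adds that the incidence of ≥ "Grade 3 laboratory abnormalities under treatment and shifts in toxicity grading from baseline to highest grade post-baseline will be displayed". Neither sentence is limited by type of visit.

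On the grading scale, SAP 3.9.1 names CTCAE v5.0 for adverse events, and SAP 3.9.2 names it for the laboratory shift tables. Protocol 9.1, 16.1, 16.3.7 and 17.5 name v4.03 for laboratory results, toxicities and adverse events.

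**The concern.** A worst-grade table is only as complete as the set of values searched for the worst. Protocol 9.1 links unscheduled visits to significant changes from baseline, and 8.7 allows hematology and chemistry to be drawn at them. These draws are more likely than routine ones to hold an abnormal value. A programmer who follows SAP 3.9 to the letter drops them; one who follows 3.9.2 to the letter keeps them. The SAP does not say which rule governs, so two competent teams could produce different tables from the same data.

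Safety and tolerability is a primary objective, and with 16 subjects per cohort a single subject is visible in the percentages.

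The CTCAE point is separate. Sites are told to assign adverse event grades under v4.03, yet the SAP describes those grades as v5.0 and applies v5.0 to laboratory values. Taken as written, the report would either mislabel the site-assigned grades or present adverse events and laboratory values on different scales.

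**Working it through.** The plan states no figure on this point, so there is none to reproduce. The check compares the texts and then works out direction and weight.

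**Tables concerned (SAP Table 6).** Worst on-treatment grade for hematology and for biochemistry, plus CTC-grade shift for hematology and for biochemistry: 2 + 2 = 4 tables.

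**Direction.** Let *S* be a subject's scheduled post-baseline grades and *U* the unscheduled ones. The title of the table calls for max(*S* ∪ *U*). Literal use of 3.9 gives max(*S*). Since max(*S*) ≤ max(*S* ∪ *U*), the omission can lower the tabulated worst grade or leave it unchanged; it cannot raise it.

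**Weight per affected subject (planned sizes 16 and 48).**
- One cohort: 1/16 = 0.0625, or 6.25 percentage points.
- Overall column: 1/48 = 0.0208, or 2.1 points.
- The subject leaves the higher-grade row and enters a lower one; the row total does not change.
- If the missed peak is Grade ≥ 3 and every scheduled value is Grade ≤ 2, the cohort's Grade ≥ 3 laboratory incidence is low by 6.25 points for each such subject.

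**Illustration under an assumption.** The documents do not give the chance *q* that a subject who truly reached Grade ≥ 3 did so only at an unscheduled draw. Suppose *k* of 16 subjects truly reached it, independently of one another. The expected number shown is *k*(1 − *q*), and the chance of missing at least one is 1 − (1 − *q*)^*k*.

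| *k* (true rate) | *q* | Expected shown | Shown rate | Chance ≥ 1 missed |
|---|---|---|---|---|
| 2 (12.5%) | 10% | 1.8 | 11.25% | 19% |
| 2 (12.5%) | 25% | 1.5 | 9.4% | 44% |
| 2 (12.5%) | 50% | 1.0 | 6.25% | 75% |
| 4 (25%) | 10% | 3.6 | 22.5% | 34% |
| 4 (25%) | 25% | 3.0 | 18.75% | 68% |
| 4 (25%) | 50% | 2.0 | 12.5% | 94% |

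At *q* = 0 nothing is lost. The documents do not exclude that.

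**Will unscheduled draws occur?** Consecutive scheduled Day 1 visits from Cycle 2 are 28 days apart, each with a ±3-day window, so at least 28 − 3 − 3 = 22 days. From Cycle 25, without the optional even-cycle visit, the gap is at least 56 − 3 − 3 = 50 days. Protocol 14.4 limits a pause to 14 days and ties resumption to recovery to at least Grade 1. A laboratory-based pause that starts at one of these Day 1 visits therefore needs a draw before the next one if dosing is to resume. Both gaps hold only between Day 1 visits. The end-of-treatment visit (protocol 8.5) is also scheduled, includes hematology and chemistry, and can fall anywhere in a cycle.

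**CTCAE.** The SAP's document history gives no reason for v5.0. The SAP cites protocol Amendment 6, and the protocol at hand is Amendment 7, but the Amendment 7 change log shows no change of CTCAE version. The amendment gap therefore does not explain the mismatch.

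**The case against.** The best defence is that SAP 3.9 is a display rule for by-visit tables. A worst-grade or shift table displays no visits, 3.9.2 is the more specific text, and its silence where 3.9.3 says scheduled suggests that all draws count. Moreover, the safety assessments named in 3.9 include adverse events, and nobody would drop from the tables an adverse event found at an unscheduled visit. This is a plausible account of the intent. It is not what the sentence says, and it is the reading that the fix would put in writing.

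The safeguards are also real. Protocol 9.2 makes a laboratory abnormality that changes management an adverse event, and its examples include a need for further monitoring, which may well cover a prompted repeat draw. Protocol 16.3.7 requires a new entry when a grade worsens. Most peaks that prompt action should therefore reach the adverse event tables. Weekly draws in Cycle 1 and the end-of-treatment draw narrow the gaps, and the listings keep every value. What remains is mainly peaks that prompted no action, or that fall under the exemption in protocol 16.4.1 for values in keeping with the present disease or with pre-entry results.

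Some stronger inferences are tempting but not supported:
- *The pause rule shows that peaks are missed.* It shows that extra draws occur. If the pause starts at a scheduled visit, the triggering grade is already tabulated, and the extra draw may show only recovery.
- *Baseline is distorted.* SAP 3.1.4 says "Baseline value is defined as the valid and last non-missing value obtained within 28 days prior to subject receiving the first study medication", whatever the visit type, and 3.9 does not amend it.
- *The Grade ≥ 3 analysis is missing.* Table 6 has no separate table, but the count is the sum of the Grade 3 and higher rows of the worst-grade tables.
- *Dose escalation is compromised.* Protocol 14.2 rests it on continuous monitoring, not on these tables.

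**Conclusion.** The point holds as a conflict of wording in the SAP with a one-sided consequence. Applied literally, 3.9 can only understate a subject's worst post-baseline laboratory grade, by 6.25 points of a 16-subject cohort (2.1 points of 48) per affected subject, across four planned tables and the Grade ≥ 3 incidence read from them. This assumes the planned cohort sizes and a literal reading of 3.9. How many subjects are affected is unknown and may be zero, so no overall bias is claimed.

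The CTCAE mismatch stands on its own. The SAP and the protocol name different versions for the same grades, without a reason or a regrading plan. A reader might infer that v5.0 would inflate or deflate the reported toxicity; the documents give no basis for a direction or a size.

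Both matters deserve correction because they determine what the safety tables report. Neither calls the conduct of the trial into question.

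**What to change.** In SAP 3.9, replace the sentence with: *Unscheduled results are excluded from by-visit descriptive summaries only. The worst-grade and shift laboratory tables, and the Grade ≥ 3 laboratory incidence read from them, use all valid post-baseline results, scheduled and unscheduled.*

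In SAP 3.9.1 and 3.9.2, replace CTCAE v5.0 with the protocol's v4.03, or keep v5.0 with a stated justification and a plan for regrading what sites recorded under v4.03.

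Optional clarifications: a separate Grade ≥ 3 laboratory table in Table 6; one time window for these tables, since the protocol speaks of on-study after the first dose and the SAP of on-treatment; and a line confirming that baseline under 3.1.4 may come from an unscheduled pre-dose draw.

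The cost is text edits in three SAP sections and minor programming; no new data are needed. Under the first edit alone, a subject's worst grade can stay the same or rise, so lower-grade rows may lose subjects to higher ones. No such direction can be given for the CTCAE edit.

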#### **3.9.1 Adverse Events**

AEs will be coded using the MedDRA dictionary (Version 20.1 or higher). Treatment-emergent AEs (TEAEs) are any AE occurring or worsening in severity after the first administration of study medication. All AEs (including SAEs) will be graded using the 5-point Common Terminology Criteria for Adverse Events (CTCAE) V5.0 scale (mild, moderate, severe, life-threatening, or death). Causality with KD025 will be classified as: definitely related; probably related; possibly related; unlikely related; or not related.

The investigator will further assess the relationship of AEs to cGVHD or the underlying disease.

The number and percentage of patients who experienced at least one TEAE as well as the number and percentage of patients who experienced AEs of each specific SOC and PT will be presented. For the presentation of AE incidences, the SOCs and the PTs within each SOC will be presented by decreasing total frequency. Tabulation by maximum severity and relationship to KD025 will also be included by treatment group.

The TEAEs, Grade  $\geq 3$  TEAEs, SAEs, and TEAEs leading to dose modification/discontinuation will be summarized by treatment arm, SOC, and PT. These analyses will be repeated for events considered related (definitely related/probably related/possibly related) to KD025.

Subject listings will be provided for SAEs, AEs resulting in study drug discontinuation and deaths.

Adverse events will also be presented in listings. Time to onset and duration of AEs will be included in listings, along with action taken and outcome.

### **3.9.2 Clinical Laboratory Evaluation**

The summary statistics (including number, mean, standard deviation, median, minimum and maximum) of all laboratory variables and changes from baseline will be calculated for each visit or study assessment by treatment group. For parameters of white blood cell counts, neutrophils (absolute count), lymphocytes (absolute count), monocytes (absolute count), hemoglobin, platelets, ALP, ALT, aspartate aminotransaminase, gamma glutamyl transferase, total bilirubin, glomerular filtration rate, plots of mean/mean changes from baseline with the corresponding standard error will be displayed.

For shift tables, laboratory results will be classified using the CTCAE Version 5.0. All graded laboratory parameters will be summarized separately for hematology and biochemistry. Corresponding shift tables comparing baseline to the worst post-baseline grade within the treatment period will be provided.

